8.3 Clinical Study Reporting

Due to relatively short duration of the clinical investigation no interim analyses will be performed. Final report to the local ethics committee and authority will be send within the required time window upon the termination or completion.

 Clinical Investigation Plan PL-RIS01	Page no.	42 z 55
	Version	02
	Date	2023-07-18

9 Data management

Data Management procedures will follow applicable regulations, all details will be separately described in a study-specific Data Management Plan (DMP) prepared by the responsible data manager (DM) and finalized and signed by both DM and designee of Perfect Lens, LLC to the start of data entry for the first enrolled patient.

9.1 Ownership of the data

All the data or results from this study are the property of Perfect Lens, LLC.

9.2 Data reporting

All data will be collected using worksheets or into the medical documentation of the patients. A validated electronic data capture (EDC) system will be used for data entry. Access to the EDC application is through a secure website connected to a dedicated server. Each study team member will have a password-protected login with a unique username for individual identification. Access rights will be assigned based on pre-defined user roles relevant to their specific tasks in the clinical investigation.

Worksheets for preoperative, surgery, and postoperative visits will be provided if needed. These worksheets will align with the data entry pages (eCRFs) in the EDC system, serving as the source data when used by the site. Corrections to the worksheets or other source data will be made by crossing out the incorrect entry, recording the correct information, and initialling and dating the change. Both the study worksheets and the data entered into the EDC system will be audited by the Study Monitor.

Data entry into the EDC system will be pseudonymized, with each subject identified by a subject code rather than revealing the actual patient's identity. The EDC system will maintain an electronic audit trail for change control. Online checks for completeness and consistency will be performed during data entry, complemented by manual quality control from the data manager. System queries will be generated, and responses must be addressed within the EDC system.

The EDC system and data will be in the English language. Investigators will receive training on the impact of missing data on the integrity and credibility of the clinical investigation to minimize instances of missing data. To maintain data completeness and accuracy, computerized data checks will identify unusual entries for verification before statistical analysis. Any queries resulting from consistency checks will be addressed by the investigator or designee within the EDC system.

9.3 Data monitoring

Study monitor will review the source documentation to ensure participants safety and the data integrity. The monitoring will be performed as per the sponsor monitoring plan.

9.4 Clinical investigation report

Upon the conclusion or premature termination of the study, a comprehensive report will be prepared. The responsibility of drafting these reports lies with the sponsor, who will

 PERFECT LENS PL-RIS01	Clinical Investigation Plan	Page no.	43 z 55
		Version	02
		Date	2023-07-18

collaborate with the coordinating investigator. Both parties are required to sign off on the reports.

In accordance with article 77(5) of the Medical Device Regulation (MDR), the clinical investigation report must be submitted within one year from the conclusion of the investigation or within 3 months if there is an early termination or temporary halt. The submission process to Ethic Committees and Authorities will be conducted in compliance with the local requirements.

9.5 Filling and archiving

The principal investigator bears the responsibility for organizing and maintaining all documents pertinent to the clinical investigation at their site. On the other hand, the sponsor is accountable for managing all sponsor-related documents, including the trial master file, the clinical investigational report, and associated data.

Following the conclusion of the clinical investigation, whether it reaches its intended completion or ends prematurely, essential clinical investigation documents must be securely archived and kept confidentially for a minimum of 15 years. This archival obligation applies both to the investigator and to the sponsor.

 PERFECT LENS	Clinical Investigation Plan	Page no.	44 z 55
PL-RIS01		Version	02
		Date	2023-07-18

10 Amendments to the Clinical Investigation Plan

Throughout the course of the clinical investigation, necessary amendments might be made to the Investigator's Brochure (IB), Clinical Investigation Plan (CIP), Case Report Forms (CRFs), informed consent form, subject information, and other relevant clinical investigation documents. Each amended section of a document will be accompanied by a justification statement to provide a clear rationale for the changes made.

Proposed amendments to the CIP will be collaboratively agreed upon between the sponsor and the investigators. These amendments, along with any modifications to the subject's informed consent form, will be promptly notified to and approved by the Ethics Committee (EC) and regulatory authorities.

To facilitate transparency and clarity, in addition to the clean version of the documents, a redlined version in change tracking mode will be submitted, clearly highlighting the modifications made. This ensures that all parties involved can easily identify and review the specific changes.

It is essential to maintain a comprehensive record of the version number and date for each amendment made. This documentation helps track the evolution of the documents over time and ensures proper version control. Only after receiving approval or notification from the relevant authority or Ethics Committee, the new version of the documents will be distributed to each investigational site and implemented in the study.

11 Deviations from the Clinical Investigation Plan

The sponsor or investigator will ensure that the Ethics Committee and Competent Authority are promptly notified of any protocol changes in accordance with relevant regulations and established procedures of the Ethics Committee/Competent Authority. Investigators are not permitted to deviate from the protocol without written approval from the Ethics Committee/Competent Authority and the sponsor, except in cases of medical emergencies where the investigator must exercise judgment to remove the subject from immediate harm. Any significant changes or deviations from the protocol will require a protocol amendment, which must be pre-approved by the Ethics Committee.

In the event of an unexpected protocol deviation, the investigator must immediately inform the sponsor, and the deviation will be documented. If necessary, site staff will undergo re-training on the specific topics to prevent future deviations.

The sponsor is responsible for classifying each protocol deviation as major or minor. Major protocol deviations are those that could substantially impact the completeness, accuracy, and/or reliability of the study data, or significantly affect a subject's rights, safety, or well-being. Examples of major protocol deviations may include enrolling subjects who do not meet key eligibility criteria or failing to collect necessary data for interpreting primary endpoints. Minor protocol deviations include visits conducted outside the specified time window, missed ancillary measurements in subjects who did not return for visits, or incorrectly performed ancillary measurements. Additional details regarding the classification of protocol deviations will be provided in the study-specific Monitoring plan.

 PERFECT LENS	Clinical Investigation Plan	Page no.	45 z 55
		Version	02
		Date	2023-07-18

During the Data Review Meeting (DRM) protocol deviations will be reclassified as major/minor or critical/non-critical for the purpose of allocating subjects to the per-protocol cohorts on both eye- and subject-level. Only protocol deviations that could impact the evaluation of primary endpoints will be considered major when determining the allocation to analysis sets.

Unless otherwise required, only major protocol deviations with safety implications will be reported to the local Ethics Committee, including those that could potentially affect patient safety.

12 Device accountability

The device will be provided by the sponsor who will install and calibrate the device at the site.

The process of installation and, if applicable, de-installation will be meticulously documented in installation/de-installation reports. Copies of these reports will be stored in both the investigator site file (ISF) and the trial master file (TMF) for proper record-keeping. The original reports will be securely filed to ensure their safekeeping and accessibility.

13 Compliance

This clinical investigation will be conducted in strict adherence to the relevant recommendations established by the 18th World Medical Assembly in Helsinki, Finland, in 1964, as well as subsequent revisions. It will also adhere to the European Committee for Standardization ISO 14155, which sets the standard for clinical investigation. Additionally, all applicable local and national regulations will be followed.

All parties involved in the conduct of the clinical investigation bear the responsibility for ensuring its ethical conduct, as per their respective roles. This includes obtaining approval from the Ethics Committee (IEC)/Institutional Review Board (IRB) and Competent Authority, obtaining prospective informed consent, monitoring the investigation's progress, ensuring the accuracy of data entered into the Electronic Data Capture (EDC) system or other employed methods, which may be carried out by the Sponsor or its designated representatives. The Sponsor will also retain records in accordance with MPKPV §10 section (7) and Regulation (EU) 2017/745 (MDR), Chapter VI, and Annex XV.

Furthermore, all parties involved will comply with the EU General Data Protection Regulation 2016/679 (GDPR) and the relevant national Data Protection Regulation. Data protection and privacy measures will be strictly followed to ensure compliance with these regulations.

The Sponsor holds the responsibility of obtaining the necessary approvals from the Ethics Committee (EC) and Competent Authority on behalf of the investigator before commencing subject enrolment in the clinical investigation. Additionally, the Sponsor is required to keep both the EC and Competent Authority informed about any serious side effects or adverse events that occur during the study, as well as any amendments made to the protocol.

The Principal Investigator at each investigational site bears the responsibility for ensuring the

CONFIDENTIAL

 PERFECT LENS PL-RIS01	Clinical Investigation Plan	Page no.	46 z 55
		Version	02
		Date	2023-07-18

proper conduct of the study in accordance with the aforementioned regulations, guidance documents, clinical study agreement, protocol (including amendments), and any additional conditions imposed by the reviewing EC, if applicable. The Principal Investigator must ensure the presence of an adequate number of qualified personnel and the availability of necessary facilities for the entire duration of the study, in order to conduct the investigation safely and appropriately. Furthermore, the Principal Investigator must ensure that all personnel involved in the investigation receive sufficient training on the protocol, investigational products, and their respective responsibilities and roles within the study.

The study must be carried out in accordance with the Standard Operating Procedures (SOPs) of the Sponsor or the delegated Contract Research Organization (CRO), as well as all other relevant regulations that apply to the investigation.

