6.2 Anticipated risks

6.2.1 Primary Safety Analysis

The risks to the patients and the steps taken by Perfect to obviate those risks are set forth in the Risk Management Study attached as Exhibit A.

The principal risk to the patients is an injury from the laser energy. The last 12 patients treated using the Device in the Panama Study had no Adverse Events. The energy to be used in this study is less than the energy used in the human study in Panama where there was no injury and is less than 10% of the energy used when a patient has a serious Adverse Event from excess energy to the retina.

A second risk is that the IOL moves during the Treatment. If there is movement of the IOL Treatment is not effective. The Device and its components have been further stabilized to reduce the risk of movement. In addition, an IOL tracking system has been implemented to allow the operator to compensate for movement should it occur.

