7.1 Study design

This is a prospective non-randomized patient controlled single centre design pilot clinical trial. One Study Cohort is planned with up to 12 patients and up to 24 eyes. The post Treatment eyes will be compared to the pre-Treatment eyes to determine if endpoints have been met. The study will treat both eyes of a patient to ensure that the patient has effective multi focal vision. The Treatment for both eyes may be on the same day, assuming there are no issues with the first Treatment.

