7.2 Endpoints

There are three co-primary effectiveness endpoints at the 1-month post Treatment visit.

Distance Corrected Near Visual Acuity (DCNVA) at 40 cm. The hypothesis tested for is to demonstrate superiority of the near vision of treated IOL to the IOL pre-Treatment.

Distance Corrected Intermediate Visual Acuity (DCIVA) at 66 cm. The hypothesis tested for is to demonstrate non-inferiority of the treated IOL to the pre-treated IOL (using a non-inferiority margin of 0.10 logMAR).

Best corrected distance visual acuity (CDVA) at 4m. The hypothesis tested for the co-primary effectiveness endpoint #3 is to demonstrate non-inferiority of the treated IOL to the pre-Treatment IOL (using a non-inferiority margin of 0.10 logMAR).

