7.5 Comparator (control) arm

No comparator (control) arm is used in this investigation.

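### Deviations may be reclassified to form the per-protocol cohorts with no safeguard against acuity results being known, in an unmasked, uncontrolled study of up to 12 patients

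*Protocol*

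**What the plan says.** Section 11 sets up two rounds of classification. In the first, "The sponsor is responsible for classifying each protocol deviation as major or minor". In the second, at a Data Review Meeting, "protocol deviations will be reclassified as major/minor or critical/non-critical for the purpose of allocating subjects to the per-protocol cohorts", at both eye and subject level. One limit follows: "Only protocol deviations that could impact the evaluation of primary endpoints will be considered major when determining the allocation to analysis sets". The section gives examples of major and minor deviations (an out-of-window visit is minor) and adds that "Additional details regarding the classification of protocol deviations will be provided in the study-specific Monitoring plan". It does not say when the meeting takes place, who attends, or whether attendees have seen the acuity data.

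On design, section 7.1 states that "One Study Cohort is planned with up to 12 patients and up to 24 eyes" and that eyes after treatment are compared with the same eyes before treatment. Section 7.5 states that "No comparator (control) arm is used in this investigation". No masking is described. Section 7.2 names three co-primary endpoints at 1 month: superiority for distance-corrected near acuity (DCNVA), and non-inferiority for distance-corrected intermediate acuity (DCIVA) and corrected distance acuity (CDVA), both "using a non-inferiority margin of 0.10 logMAR".

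Section 8.2 plans descriptive statistics only. It refers to a specified population without naming one. Section 7.16.1 keeps discontinued subjects in the analysis up to their exit.

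**The concern.** Sorting deviations at a data review meeting is ordinary practice. It protects the result when those who decide cannot tell how a decision moves the comparison. Here each patient's baseline and 1-month acuity together are the comparison, so anyone who has seen a patient's results knows which way that patient's exclusion would move the summary. No control arm would reveal a tilt.

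The protocol does not require an independent person in the reclassification. The sponsor makes the first classification (section 11), supplies the device operators and the data monitor (section 3) and drafts the report (section 9.4).

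The endpoint-relevance limit leaves room for judgement. A late 1-month visit is minor among the section 11 examples, yet it falls at the primary time point and could be argued to affect the primary endpoints. Section 6.2.1 also names a known cause of failure: "If there is movement of the IOL Treatment is not effective". Nothing in section 11 settles whether a treatment disturbed by movement could be recorded as a procedural deviation. If it were, the per-protocol cohort would lose the device failures that a pilot study most needs to count.

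**Working it through.** The protocol gives no alpha, power, effect size or SD (section 8.1 says no sample size calculation was performed), so there is no planned figure to reproduce. The checks below show only how sensitive a 12-patient summary is to one or two exclusions. The inputs from the protocol are n = 12 patients (sections 7.1 and 8.1) and the 0.10 logMAR margin (section 7.2). Everything else is assumed.

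**1. Shift in the mean change, worst case.** Assume 12 independent normal changes with SD 1, with the worst one or two removed because they are the worst. The expected values of the two lowest of 12 standard normal values are −1.629 and −1.116.

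- Worst 1 removed: shift = 1.629 / 11 = 0.148 SD.
- Worst 2 removed: shift = (1.629 + 1.116) / 10 = 0.274 SD.

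Simulation agrees (0.149 and 0.275 SD). With no true effect, a one-sided 2.5% t-test on the remaining patients would reject in 8.5% and about 18% of runs. Section 8.2 plans no such test, so these rates are illustrative. They apply directly to superiority; for the non-inferiority endpoints they apply to the change measured from the margin.

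**2. Proportion successful** (number of failures assumed; Clopper-Pearson 95% lower limit).

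| Failures | All 12 treated | Lower limit | Failures excluded | Lower limit |
|---|---|---|---|---|
| 1 | 11/12 = 91.7% | 61.5% | 11/11 = 100% | 71.5% |
| 2 | 10/12 = 83.3% | 51.6% | 10/10 = 100% | 69.2% |
| 3 | 9/12 = 75.0% | 42.8% | 9/9 = 100% | 66.4% |

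**3. DCNVA gain** (assumed 0.30 logMAR in successes, 0 in failures). The mean over all 12 is 0.30 × (12 − f)/12, which gives 0.275, 0.250 and 0.225 for f = 1, 2 and 3 failures. With the failures excluded it is 0.30 in each case.

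**4. CDVA loss against the 0.10 margin** (assumed mean 0.02 and SD 0.06 in the unaffected patients; upper limit = mean + t(0.975, n − 1) × SD/√n).

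- One patient loses 0.30. All 12: mean = (11 × 0.02 + 0.30)/12 = 0.043, SD = 0.099, upper limit = 0.043 + 2.201 × 0.099/√12 = 0.106, outside the margin. Without that patient: 0.02 + 2.228 × 0.06/√11 = 0.060, inside.
- One patient loses 0.20. Upper limit 0.084 with all 12, 0.060 without that patient; both inside.
- Two patients lose 0.20. Upper limit 0.106 with all 12, outside; 0.063 without them, inside.

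So one or two exclusions can change the side of the margin on which the limit falls, though not under every assumption.

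**The case against.** The strongest reply is that section 11 is already restrictive. Exclusion needs a recorded deviation that could affect the primary endpoints; a poor result alone does not qualify. The general class of major deviations also covers those touching rights or safety, so reclassification may narrow that class and exclude fewer people. Further detail is promised in the Monitoring plan, and ranking the analysis sets is commonly left to a statistical analysis plan; neither document is at hand. The study is a descriptive pilot, so error rates for an assumed test measure something that is not planned.

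Most of this stands and limits the point. Two stronger readings are tempting and are not supported:

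- A reader might infer that the meeting takes place when every outcome is known. Section 11 gives neither its timing nor its access to data. The open design makes prior knowledge likely, but that is inference.
- A reader might infer that failures will be taken out of the study's main result, or that IOL movement will be treated as a deviation. No section makes per-protocol the primary result, section 7.16.1 keeps discontinued subjects in up to exit, and no section calls movement a deviation.

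The reply does not supply a safeguard. The limit is a criterion to be judged case by case, and the reclassification step stays in the protocol whatever the Monitoring plan adds. Section 7.16.1 covers patients who leave the study, not treated patients moved out of a per-protocol cohort.

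**Conclusion.** The point holds as a weakness in a rule that the protocol states, not as evidence of a biased plan. In an unmasked, uncontrolled study of up to 12 patients, section 11 allows membership of the only named analysis set to be revised at a meeting with no bar on knowing the acuity results and no closed list of excluding deviations.

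At worst the mean change shifts by about 0.15 SD for one exclusion or 0.27 SD for two. That bound assumes independent normal changes and deliberate removal of exactly the worst patients, each with an endpoint-relevant deviation; exclusions unrelated to outcome would have no systematic effect. The success proportions and CDVA limits rest on assumed data. The shifts in means and proportions matter for a descriptive report as well; the error rates would matter only if a test were added. The change is worth making because it is cheap and the study is small.

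**What to change.** In section 11, keep the limit to deviations that could affect the primary endpoints, but fix the list of excluding deviations, per eye and per subject, before the first 1-month acuity is recorded. Have the Data Review Meeting only apply that list. Document any unforeseen deviation together with the reason for how it was handled.

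In section 8.2, report the three co-primary endpoints on all treated eyes and patients with data as the main result, with the per-protocol result beside it. State, for the analysis sets only, that IOL movement or an incomplete treatment effect is a device outcome and not in itself a ground for exclusion.

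The cost is about a paragraph of wording, with no change to visits or procedures. The downside is that the reported figures may be slightly less favourable, because failed treatments stay in.

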13.1 Insurance

For the purpose of this clinical investigation, a specific insurance policy will be obtained to cover subjects for clinical-investigation-related risks arising from their participation.

Additionally, an insurance policy for commuting accidents will also be contracted. It is important to note that the responsibility for arranging these insurance policies lies with the sponsor, Perfect Lens. Prior to signing the patient informed consent, all subjects will receive detailed information regarding the insurance coverage.

The primary contact for the insurance provider is as follows:

HDI Versicherung AG, organizační složka
 [name]
 [name]
 [contact]
 [contact]
 E-Mail: [contact]

HDI is responsible for providing national insurance certificates. The sponsor must submit these certificates to the Ethics Committee before the study commences. A copy of the certificates will be included in the Investigator Site File. It is crucial to emphasize that patients will only be insured after they have signed the consent form. Patients who undergo preoperative examinations that are consistent with the regular practices of refractive laser surgery clinics will not be covered by this insurance if they are only undergoing screening and not participating in the full study.

